Patients were selected among those who had applied to emergency service and evaluated by a pulmonary medicine resident or specialist. The general population of the study was made from the patients whose hospital admission to the COVID-19 ward was required after pulmonary medicine evaluation requested by an emergency medicine specialist. Inclusion criteria were being over 18 years old, approval given both written and orally for participation, COVID-19 positivity proven by reverse transcription-polymerase chain reaction (RT-PCR) testing, and deemed suitable for pulmonary function testing by a pulmonary medicine specialist. Exclusion criteria were planned mostly for optimal function testing, which included any pathological findings that impede pulmonary function testing such as chest deformity, an additional persistent pulmonary pathology that would prevent hospital discharge even after COVID-19 treatment, known severe pulmonary function loss (characterized by a FEV1 of %30 or less or being unable to participate in respiratory function testing), persistent COVID-19 findings which may affect respiratory functions (characterized by being bedridden or extended stay requirement due to desaturation not responding to nasal oxygen therapy) and former COVID-19 history.

Due to ethical considerations and the assumption that respiratory physiotherapy performed by the respiratory exerciser would be beneficial, all patients accepted into the study were offered enlistment to the treatment group. Those willing to participate in the study but refused device usage were accepted as the control group. Patients in the treatment group were asked to use the respiratory exerciser at least four times per day, with each session not lasting longer than 10 minutes and with at least an hour in between sessions.

Regardless of suitability for the study, all patients undergo a respiratory function test evaluation at the end of the first month, as per routine hospital approach to COVID-19 patients requiring hospital admission. The follow-up results of those who had participated were recorded from this evaluation. Additional follow-up was performed as a part of routine COVID-19 follow-up, such as an RFT at three months; however, these results were not a part of this study and thus were not accessed or recorded.

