PEF, as both percentile and absolute value change, was accepted as the study's primary outcome. Mortality was considered as the secondary outcome parameter. The presence of known respiratory diseases was accepted as the main confounding parameter, and thus, as defined earlier, patients with known respiratory limitations had to be removed from the study. Other comorbidities were evaluated by Charlson Comorbidity Index (CCI). Forced Expiratory Volume (FEV) and Forced Vital Capacity (FVC) percentages were used to confirm the respiratory stability before COVID-19 diagnosis, values of both being over 80% was deemed normal. Demographic data was also included due to being required to calculate respiratory function thresholds.

Patients' data were retrieved from the hospital record system and from the respiratory function testing center. Demographic data, treatment modalities, and evaluation dates were also evaluated from electrical patient files from the hospital record system. Initial PEF results were taken from the patients' personal peak flow meter devices, and the final results were recorded from both hospital spirometer results and personal devices. Retesting was performed when a difference above 10% was observed between two different methods. If a difference was to be observed again, the result from the patient's device was accepted as the end result.

Selection bias was the main expected bias, and it was expected to be lessened by offering participation to all patients admitted to the COVID-19 ward. However, due to the study design, patients whose status was considered stable for outpatient treatment were excluded, which was expected to affect the results in favor of the treatment group. Additional treatment requirements were also considered another source of bias, as patients admitted to the COVID-19 ward often received more intensive treatment than outpatient regimens. However, the treatment regimen given to those admitted to the ward, which the study population consisted of, was assumed to be the same. Similarly, a combination of comorbidities was also considered another bias that might hinder a patient's ability to participate in respiratory testing, regardless of former capacity; thus, Charlson Comorbidity Index (CCI) was used to investigate comorbidities and ensure that comorbidities are present that patients remain within an acceptable range.

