A total of 50 patients were assumed to be recruited into the study, with an even distribution between control and treatment groups. Excluding respiratory function test results, no further quantitative variable grouping was performed.

Descriptive analyses were utilized for data presentation. Nonparametric testing was utilized due to non-standard distribution and reduced sample size. Mann-Whitney U test was used to evaluate the distribution patterns between groups. Spearman's rho was utilized for correlation analysis. No subgroup analyses were planned for the study. If a patient had a missing PEF value for any reason, the patient would be removed from the study regardless of other values. As the second value of PEF would be recorded at the follow-up, any loss to follow-up would also be a reason for exclusion. IBM SPSS Statistics 25th Edition was used as the statistical program.

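### Controls are patients who refused the device, yet the only planned group comparison is unadjusted, and the selection-bias safeguard acts on study entry, not on device choice

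*Combined protocol and SAP*

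**What the plan says.** The document has an Introduction and a Methods section; all the points below except the hypothesis are in Methods.

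- **Group formation.** All enrolled patients are offered the device. "Those willing to participate in the study but refused device usage were accepted as the control group". There is no randomisation.
- **Safeguard.** Selection bias is named as the bias expected most, and the plan says that "it was expected to be lessened by offering participation to all patients admitted to the COVID-19 ward".
- **Other control of confounding.** Patients with known respiratory limitation are removed. The Charlson index is used to keep comorbidity within an acceptable range. Acute severity is limited by excluding patients with persistent findings, defined as "being bedridden or extended stay requirement due to desaturation not responding to nasal oxygen therapy". On lung function before infection, "Forced Expiratory Volume (FEV) and Forced Vital Capacity (FVC) percentages were used to confirm the respiratory stability before COVID-19 diagnosis". On concomitant treatment, "the treatment regimen given to those admitted to the ward, which the study population consisted of, was assumed to be the same", although the data-source paragraph also says: "Demographic data, treatment modalities, and evaluation dates were also evaluated from electrical patient files from the hospital record system".
- **Outcome.** The primary outcome is change in PEF, on a percentile and an absolute scale. The Introduction's hypothesis is that successful users of a device have better PEF at one month.
- **Analysis.** "Mann-Whitney U test was used to evaluate the distribution patterns between groups". The other methods are descriptive statistics and Spearman's rho, and no subgroup analyses are planned. No regression, matching, stratification or weighting is described, and no effect estimate with a confidence interval.

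**The concern.** The hypothesis rests on comparing patients who accepted the device with patients who declined it. Those who accept may differ from those who decline in age, comorbidity, illness severity or motivation, and some of these may affect how PEF recovers. A test without covariates cannot separate such differences from a device effect.

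The plan names selection bias as its chief threat, but its remedy does not reach this contrast. Inviting every ward patient bears on who is in the study. The patient's later choice about the device decides which group that patient is in. Offering the device to everyone is what makes the groups self-selected.

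At stake is the reading of the primary result: a significant difference could be credited to the device when it reflects who accepts one. Charlson index and demographic data are recorded but not used in the comparison.

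**Working it through.** **What the plan's figures allow.** No figure in the plan measures this bias, so there is none to reproduce. The planned 50 patients, evenly split, enter below only as 25 per group. Everything else numerical is an assumption.

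**Does the safeguard reach the contrast?** Two choices lead to a group: joining the study, then accepting or refusing the device. The invitation to all ward patients acts on the first. The respiratory, comorbidity and severity restrictions also act at entry; they narrow the population but do not balance the groups within it. Only the change score acts within the comparison.

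**What does the change score remove?** Assumptions: no device effect; a recorded covariate differs between groups by d = 0.5 SD; it shifts one-month PEF by s = 0.3 to 0.5 SD per SD and baseline PEF by k times as much; the baseline-to-follow-up correlation ρ is 0.5 to 0.7; two-sided 5% test.

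- Bias in change = s × d × (1 − k)
- SD of change = √[2(1 − ρ) + s²(1 − k)²]
- Shift δ = bias / (SD × √(2/25)), with √(2/25) = 0.283
- False-positive rate ≈ Φ(δ − 1.96) + Φ(−δ − 1.96)

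The low row of each pair uses s = 0.3, ρ = 0.5; the high row uses s = 0.5, ρ = 0.7.

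| Covariate affects | Bias (SD) | SD of change | δ | Normal approximation | Mann-Whitney, simulated |
|---|---|---|---|---|---|
| One-month PEF only (k = 0), low | 0.3×0.5×1 = 0.15 | √1.09 = 1.044 | 0.51 | 8.0% | about 7% |
| Same, high | 0.5×0.5×1 = 0.25 | √0.85 = 0.922 | 0.96 | 16.0% | about 16% |
| Baseline half as much (k = 0.5), low | 0.075 | √1.0225 = 1.011 | 0.26 | 5.8% | about 5% |
| Same, high | 0.125 | √0.6625 = 0.814 | 0.54 | 8.4% | about 9% |
| Both visits equally (k = 1) | 0 | – | 0 | 5.0% | about 5% |

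The simulated column gives the ends of the range over ρ and over normal and skewed errors. Regression adjusted for the covariate stays at about 5% in all three cases with ordinary standard errors, and at about 3-4% with HC3 robust errors.

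**A gap in baseline PEF itself (d = 0.5 SD).**

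- If both groups regress to a common mean, the expected follow-up gap is ρd, so the change score is biased by ρd − d = −(1 − ρ)d, or 0.15 to 0.25 SD in size. Mann-Whitney on change gives 10-16% and covariate-adjusted change 10-14%. The model with baseline PEF as a covariate (ANCOVA) gives about 5%.
- If the gap is stable, it stays at d. ANCOVA removes only ρd and is biased by (1 − ρ)d, giving 10-16%. Both change analyses give about 5%.

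Neither model is right in both cases.

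**An unrecorded factor (d = 0.5, s = 0.3 to 0.5, one-month PEF only).** Mann-Whitney on change gives 7-17% and the adjusted models 7-18%. Adjustment gives no protection here.

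**The case against.** The strongest objection is that the planned analysis already does much of the work. The primary outcome is change, and age and sex are fixed over a month. The plan itself ties demographic data to respiratory function thresholds, so these traits plausibly shift PEF at both visits. If they do so equally, Mann-Whitney on change is not inflated. This stands, and three stronger readings that a reader might draw do not hold:

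- *That the plan has no control of confounding.* It restricts respiratory limitation, comorbidity and acute severity, and it scores change.
- *That 7-16% is the plan's false-positive rate.* That range needs a covariate that affects follow-up PEF and leaves baseline PEF untouched, and the documents give no sign of how large any imbalance is. Nor do they give a direction for device choice: the one direction they predict, in favour of the treatment group, concerns excluding patients fit for outpatient care.
- *That adjustment repairs the comparison.* Reasons for refusal and severity within the eligible range are not listed as recorded. If these drive acceptance, regression does not help.

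Two further objections have some force. The descriptive analyses and the Mann-Whitney test name no variables, so they may already include baseline characteristics by group; the plan should say so. And the study is labelled observational, which signals caution, but its title speaks of an effect and its hypothesis is about device benefit.

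None of this answers the central point. The change score does not remove confounding by factors that affect recovery, or by a baseline gap that regresses to a common mean, and the stated safeguard does not act on device choice.

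**Conclusion.** The concern holds in limited form. From the text alone: exposure is self-selected, the only group comparison is unadjusted, and the selection-bias safeguard acts on study entry. Following the plan as written could credit the device with differences between acceptors and refusers.

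The size and direction of that error are unknown. Under the assumptions shown, a recorded covariate takes the false-positive rate on change from about 5% to at most about 16%, depending almost wholly on whether it affects recovery or PEF level at both visits. Adjustment deals with recorded factors only, so the stated conclusion has to change along with the analysis. The documents do not show that any observed difference would be spurious, only that this analysis could not tell.

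A separate mismatch remains: the hypothesis refers to successful users, whereas the groups are defined by acceptance or refusal. The fix below does not resolve it.

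**What to change.** 1. **Main adjusted analysis.** Compare change in PEF between the device and no-device groups by linear regression with age, sex (assumed to be among the recorded demographic data) and Charlson index as covariates. Report the adjusted difference with a 95% CI from HC3 robust standard errors. HC3 suits the uncertain distribution and split: in a simulated 15/35 split with control error SD 1.5 times larger, ordinary least squares gave 8.0-8.9% false positives and HC3 4.3-5.1%. Keep Mann-Whitney as supportive. If the percentile scale means percent of predicted, say why age and sex are adjusted for again.
2. **One labelled sensitivity analysis.** Fit one-month PEF with baseline PEF added as a covariate. If the conclusion differs, say so and explain that it depends on how a baseline gap behaves.
3. **Table by group.** Show baseline PEF, age, sex, Charlson index, FEV and FVC percentages and treatment modalities. The last checks the assumption of equal ward treatment; it is not a default covariate, because its timing relative to device use is not stated.
4. **Wording.** Replace the selection-bias sentence with a statement that device use was self-selected, that unrecorded factors such as severity within the eligible range and reasons for refusal cannot be adjusted for, and that the result is an association, not a device effect.

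The document is written largely in the past tense. If outcome data have already been seen, label the adjusted analyses post hoc.

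**Cost.** No new patients or measurements. The covariates use three degrees of freedom (four with baseline PEF) out of about 50. For a true 0.5 SD difference without imbalance, simulated power with ordinary standard errors is 38-60% for both adjusted change and Mann-Whitney with normal errors, but 40-60% against 49-72% with skewed errors. HC3, being slightly conservative here, would lower the adjusted figures a little. Another package may be needed for the interval, and the conclusion will be more cautious.
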